### **13.3.2.2 SAE reporting period by the investigator**

The investigator has to report all SAEs by faxing the SAE form immediately (within 24 hours) to the authorized representative of the sponsor:

Institute of Clinical Pharmacology  
Hannover Medical School  
[name]  
[name]  
[contact]  

### **13.3.2.3 Exceptions to the SAE reporting requirements**

No exceptions.

### **13.3.2.4 Pregnancies**

Any pregnancies occurring in the intervention group within the reporting period have to be reported to:

Institute of Clinical Pharmacology  
Hannover Medical School  
[name]  
[name]  
[contact]  
**[contact]**

E-Mail: [[contact]](mailto:[contact])

Pregnancies have to be followed until an outcome of the pregnancy is documented with information about the status of both, mother and child. Any preterm termination of pregnancy has also to be reported.

### **13.3.2.5 Events associated with pharmaceutical quality**

Any defects or events that are encountered with the IMP that may be attributed to shortcomings of pharmaceutical quality must be reported to:

Institute of Clinical Pharmacology  
Hannover Medical School  
[name]  
[name]  
[contact]  

**E-mail: [[contact]](mailto:[contact])**

### **13.3.2.6 Overdosing**

Significant overdosing must be reported as a SAE by the Investigator to the sponsor. Overdose of IMP is defined by the Sponsor as administration of > 110%. E.g. ≥ 100 tablets over a period of 91 days OR > 2 tablets at any single day.

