Schedule	
Duration of the entire study (first patient in to last patient out): approximately 4.4 years
 
Study-related: Recruitment period: From March 2014 to August 2016
 
Patient-related: Duration of interventional/observational period including: 104-230 weeks

Number of patients	
Screening: Estimated to be n = 2700
 
To be included: n = 2000
 
To be randomized: n = 300
 
n = 300 patients will be randomized into intervention group with placebo or spironolactone and enter the double-blind treatment period if a CKD273 specific (high risk) proteomic pattern is observed. Patients will be stratified in the two treatment arms (1:1) based on whether or not the patients is treated with RAS blocking agents at the time of entry (Screening). The remaining patients with a negative (low risk) proteomic pattern will be observed regarding the development of microalbuminuria and will receive standard of care treatment (observational group).

Investigational medicinal products	
Investigational medicinal product (IMP):
 
Administration: orally
 
Active medication:
 
Spironolactone (potassium sparing diuretic) Dosage: 25 mg per day (One tablet once daily)
 
Placebo: Dosage: matched placebo (One tablet once daily)

Study endpoints	
Primary study endpoint: Development of confirmed microalbuminuria (UACR>30 mg/g) in at least two out of three first morning voids with <math>\geq 30\%</math> increase (geometric mean)

	
in UACR from “run-in” period samples OR > 40 mg/g (geometric mean).
 
Secondary study endpoints: Changes in albuminuria throughout the study period in all patients by assessing the slope of albuminuria.
 
Predictive value of the urinary proteomics test in regards to renal and cardiovascular events.
 
Changes in eGFR including development of eGFR < 60 ml/min/1.73m^2
 
Changes in retinopathy and frequency of laser treatment.
 
Additional scientific endpoints: The analysis will consider age and gender effects on the predictive value of the proteomics test and treatment effect.
 
Assessment of safety in the intervention group.

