#### 11.1.3 Packaging

Packages with active or place study drug will be indistinguishable from each other.

Primary packaging will contain IMP for 13 weeks of treatment plus a small overage (110 tablets).

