### 11.2 Accountability procedures for the IMP

After randomization, patients of the intervention group will receive IMP from the study site they attend.

At every 13th week after the Baseline the patients should be asked to return the IMP for accountability.

Patient should take between 80-110% of IMP to be compliant. The process for capturing the compliance information is the assessment by tablet counts at each site.

A record of all IMP movements including drug dispenses must be performed and documented by each site.

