## **18 PROTOCOL AMENDMENTS AND DEVIATIONS**

### **18.1 Protocol amendments**

Any amendment to this protocol must be approved by the sponsor and coordinating investigator. Favorable opinion of leading IEC and NCA approval will be obtained before any substantial amendment is implemented.

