6.3.2.2 Analysis of secondary endpoints

Based on a 2x2 table included the primary endpoint (event/ event free) vs. treatment allocation (active/ placebo) we will calculate numbers needed to treat and tested for significance using Chi-square test.

For Cox-regression models both unadjusted and adjusted using treatment allocation as determinant. Adjustment for age, gender, HbA_{1c}, systolic blood pressure, retinopathy, study site, eGFR and UACR at baseline will be conducted for both primary and secondary endpoints (see section 6.1.1 and 6.1.2, excluding 6.1.2 C, H and J).

For further clarification of the added value for discrimination, the rIDI will be calculated for all above described Cox-regression models with a significant HR for treatment allocation in the unadjusted model for each endpoint.

For safety outcome (section 6.2.1 J) only AE/SAE with the term hypotension, hyperkalaemia or gynaecomastia will be analysed using chi-square test.

To evaluate changes in UACR and eGFR over time (outcome measurement C and H in section 6.2.1) a linear mix model will be applied with adjustment for eGFR and UACR at baseline.

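### The overdose example (100 or more tablets in 91 days) starts one tablet below the > 110% definition it illustrates

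*Protocol*

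**What the plan says.** Protocol section 13.3.2.6 requires significant overdosing to be reported as an SAE. It then defines overdose as a percentage and gives a tablet count as an example: "Overdose of IMP is defined by the Sponsor as administration of > 110%. E.g. ≥ 100 tablets over a period of 91 days". Taking more than two tablets on any single day is given as a separate alternative.

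Three other places in the protocol bear on the same count:

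- The synopsis fixes the planned dose: "Dosage: 25 mg per day (One tablet once daily". Section 11.1.2 rules out titration.
- Section 11.2 sets the adherence range: "Patient should take between 80-110% of IMP to be compliant". Adherence is assessed by tablet count at each site.
- Section 11.1.3 describes the supply: "Primary packaging will contain IMP for 13 weeks of treatment plus a small overage (110 tablets". Thirteen weeks is 91 days, the period used in the overdose example.

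**The concern.** A worked example should give the same answer as the rule it illustrates. Here the rule is strictly above 110%, while the example begins at 100 tablets in 91 days, which is just below 110%. A patient with exactly that count is compliant under section 11.2 and an overdose case under the example in 13.3.2.6.

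The decision is a safety-reporting one, and section 13.3.2.2 requires SAEs to be reported within 24 hours. Site staff count tablets, and this is the only 13-week tablet count the protocol gives them for that decision. A site that uses the printed count and a site that works out the percentage would classify the same patient differently.

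**Working it through.** **Inputs**

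- Planned dose: one tablet a day, with no titration (Protocol synopsis; section 11.1.2).
- Period: 91 days (section 13.3.2.6), equal to the 13-week supply (section 11.1.3).
- Overdose: strictly more than 110% (section 13.3.2.6).
- Compliance: 80% to 110% (section 11.2).
- Pack size: 110 tablets (section 11.1.3).

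**Step 1: planned count.** 91 days × 1 tablet = 91 tablets = 100%.

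**Step 2: try to reproduce the printed threshold.** The upper limit is 1.10 × 91 = 100.1 tablets. The smallest whole number above 100.1 is 101, so the printed figure of 100 is not reproduced.

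**Step 3: counts on either side of the limit.**

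| Tablets in 91 days | % of plan | Above 110%? | Section 11.2 | Printed example |
|---|---|---|---|---|
| 100 | 100/91 = 109.89% | No | Compliant | Overdose |
| 101 | 101/91 = 110.99% | Yes | Not compliant | Overdose |

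The shortfall at 100 tablets is 110.00 − 109.89 = 0.11 percentage points.

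**Step 4: the full compliant range.** The lower limit is 0.80 × 91 = 72.8, so the first compliant whole count is 73 (73/91 = 80.2%). Over 91 days, section 11.2 makes 73 to 100 tablets compliant. The printed overdose range overlaps this at 100 and nowhere else.

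**Step 5: in terms of returned tablets.** From one full pack, assuming every tablet not returned was taken:

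- The definition covers 101 to 110 tablets taken, so 110 − 101 = 9 or fewer returned.
- The printed example covers 100 to 110 tablets taken, so 110 − 100 = 10 or fewer returned.

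**Step 6: could another reading give 100?**

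- A 90-day period would. The limit is 1.10 × 90 = 99.0, and 100 is then the first count above it (111.11%). But the text says 91 days, consistent with the 13-week supply.
- Rounding does not help. 109.89% rounds to 110%, and the definition needs more than 110%.

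**The case against.** The arithmetic is not in dispute; the objections concern weight.

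- **The rule is right and comes first.** The percentage definition agrees with section 11.2, and the count is offered only as an example. A site that applies the definition gets the correct answer. This stands, and it is why the point is minor.
- **The examples may be practical triggers.** Two tablets in one day is 200% of the daily dose, yet the single-day example starts only above two. On that view 100 is a convenient round number. The reading is possible, but it does not remove the conflict: a count of 100 would still be compliant in section 11.2 and an overdose in 13.3.2.6.
- **Intervals are often not 91 days.** Table 1 allows ±14 days around periodic visits, so the first interval can run from 77 to 105 days. The 110% limit then moves from 1.10 × 77 = 84.7 to 1.10 × 105 = 115.5 tablets, and one tablet is small beside that. This is a fair point about practical effect, and it limits the returned-tablet counts above to a 91-day interval. The example itself specifies 91 days, however, and at 91 days it is wrong.
- **Little follows from it.** Nine extra tablets over 13 weeks are unlikely to be judged a significant overdose, and any error adds a report instead of losing one. This also stands.

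**Conclusion.** The example is wrong as printed, by one tablet (0.11 percentage points). The first count over 91 days that meets the definition is 101, and only a count of exactly 100 is misclassified. This assumes one tablet daily throughout and a 91-day interval, both stated in the protocol. Expressing it as returned tablets also assumes one full pack and that unreturned tablets were taken.

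The importance is low, and the error is on the cautious side. Efficacy results and sample size are unaffected. The per-protocol cohort in SAP section 4.3.4 uses its own 80% to 110% accountability rule, so membership does not change. In SAP section 6.3.2.2 the safety tests are restricted: "only AE/SAE with the term hypotension, hyperkalaemia or gynaecomastia will be analysed using chi-square test". Overdose is not among those terms. The correction is worth making because the figure is a printed threshold for a reporting decision.

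**What to change.** In Protocol section 13.3.2.6, replace 100 or more tablets with 101 or more (equivalently, more than 100) over 91 days. The example then agrees with the > 110% definition and with the range in section 11.2. If the sponsor does want 100 tablets to count as an overdose, the definition has to change instead, and section 11.2 with it.

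The cost is one number, with no added data and no SAP change. Section 18.1 still applies: "Any amendment to this protocol must be approved by the sponsor and coordinating investigator". Ethics committee and authority approval is required there only for substantial amendments, and this is hard to regard as one. It does not justify an amendment of its own and can go in with the next. The SAP already describes recruitment and the safety committee reviews in the past tense (sections 3.6 and 5.3.3). If no further amendment is due, a note to sites and to file stating that the percentage definition governs would do the same job.

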### **13.3.2.7 SUSAR-Reporting by the Sponsor**

In line with the "CT-3" guideline and EU directive 2001/20/EC, it is the responsibility of the sponsor to report all SUSARs that occur in this trial to the respective competent authorities, the leading IEC, and to all investigators of the trial.

Fatal or life-threatening SUSARs must be reported within 7 days, all other SUSARs need to be reported within 15 days.

Also, all events which can change the benefit-risk ratio of the investigational medicinal product have to be reported within 15 days in the same way as SUSARs. This includes:

- Case reports of expected SARs with an unexpected outcome
- Increased incidence of SARs which is considered clinically relevant
- Cases of suspected SUSARs which occurred in patients after completion of the trial participation
- Occurrences in relationship to the trial or the IMP which might affect the safety of the patients

### **13.3.2.8 Development safety update report (DSUR)**

On an annual basis throughout the clinical trial, the sponsor or his authorized representative will provide the NCA and the leading IEC with a written safety report. The safety report's format will adhere to the ICH-guideline E2F (developmental safety update report, DSUR) and include a listing of all suspected serious adverse reactions which have occurred over this period as well as a report of the patient's safety.

## **13.4 Data monitoring committee and stopping rules**

The sponsor has the right to terminate the study at any time for reasonable medical or administrative reasons.

Stopping rules for the whole study: The Steering Committee on samples, data and ethics has the right to terminate the study at any time for reasonable medical safety reasons. The Data Monitoring Committee, which has access to safety data, will provide the Steering Committee on samples, data and ethics with recommendations on the continuation or discontinuation of the study as well as on recommendations for amendments to the study protocol.

The rules about decision finding and meeting procedures for the Data Monitoring committee will be laid out in a separate Data Monitoring Committee Charter.

## 14 RISK ASSESSMENT AND WITHDRAWAL RULES

### 14.1 Potential risks

For the patients, sample collection bare minuscule risks of infection at the venipuncture site.

Patients in the intervention groups will be randomized to placebo or spironolactone on top of standard treatment with the potential common site effects like fatigue, hyperkalemia, hyponatremia, gynecomastia and disorder of menstruation (see section 11.3)

### 14.2 Known potential benefits

Spironolactone has known diuretic effects and antihypertensive effects, although small in this dose. The applied dose has demonstrated significant beneficial effects on urinary albumin excretion in patients with elevated levels, and a beneficial effect on survival in patients with heart failure.

### 14.3 Potential benefits

The observational study will determine whether the proteomic analysis can identify patients at high risk of developing renal complications in patients with type 2 diabetes. The intervention study will determine whether spironolactone on top of conventional treatment reduces development of renal and cardiovascular complication to diabetes in normoalbuminuric type 2 diabetic patients.

### 14.4 In concurrent illness

In case of in concurrent illness or acceleration of chronic disease it will of the investigators opinion to either pause or stop the IMP permanently. In case of hyperkalemia action must be taken in accordance with appendix 1, section 24.

In case of hypotensive symptoms or measured BP below 100/50 consider temporary or permanent reduction in antihypertensive or diuretic treatment, while taking concomitant disease or dehydration into consideration.

In any case of in concurrent illness it will on the investigators opinion to pause or stop the IMP. In that case a rapport must be made in accordance with section 13.

### 14.5 Patient withdrawal

Patients have the right to withdraw voluntarily from study treatment or the entire study at any time for any reason. The investigator also has the right to withdraw patients from the study treatment and the entire study if he or she considers this to be in the best interest of the patient. Should a patient decide to withdraw, all efforts will be made to complete and report the observations as thoroughly as possible. The investigator will make every reasonable attempt to contact the patient to determine as completely as possible the reason for the withdrawal. If the reason for withdrawal of a patient from the study is an adverse event or an abnormal laboratory test result, the adverse event or test will be recorded in the eCRF.

A participant must be withdrawn if any of the following is present:

- Withdrawal of informed consent.

- Lack of adherence to the protocol as judged by the investigator.
- Simultaneous participation in another intervention study.

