#### **14.6 Criteria for discontinuation**

A participant must be discontinued in the IMP treatment if any of the following is present:

- Female patients in the intervention study who become pregnant, intend to become pregnant or do not use adequate birth control (according to inclusion criteria 7, in section 7.1).
- Experience of research-related injury or unacceptable side effects to the study medication.
- Safety considerations assessed by the investigator
- Treatment with Lithium (ATC: N05AN).
- Treatment with potassium sparing diuretics (ATC: C03D, C03E).
- Confirmed eGFR below 15 ml/min/1.73 m^2.
- Confirmed elevated liver enzyme (ASAT and/or ALT) 3 times above normal range.

Discontinued patients will be offered tests corresponding to the final study visit. Data on all patients will be included in the study and will be used in safety analysis.

After discontinuation of study medication in the randomized population, observation should continue with visits as planned in the observational group (if the patient accepts), or if that is not possible/acceptable, evaluation of vital status and development of endpoints should be evaluated through registries, information of hospitals and GPs, or interviews with the patient as appropriate and possible in order to monitor development of endpoints in all included patients as thoroughly as possible, provided that the patient agrees.

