### **24.5 Continuation of study medication**

If the potassium level is  $< 0.9$  mmol/L above upper reference range the patient can continue taking study medication.

Patients who continue study medication after temporary discontinuation of study medication must have the potassium measured according to section 24.2.5

In a patient who has experienced a potassium level of  $\geq 1.4$  mmol/L above upper reference range, and in whom the potassium fails to decrease to  $< 0.9$  mmol/L above upper reference range after the procedures described above have been tried, the study medication must be discontinued permanently and it should be recorded in the eCRF.

In case of repeated episodes of confirmed hyperkalemia after the attempt to re-start study medication following discontinuation the study medication must be discontinued permanently and it should be recorded in the eCRF.

Patients, who discontinue the study medication, will remain in the study and be followed for the full duration of the study.

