5.4 Withdrawal/ follow-up

Time of follow-up will be estimate from baseline to end – exposure time measure in day/years. Participants who withdraw will be included in the analysis with exposure time from baseline to last observation. Participants who withdraw consent are included in the statistical analysis unless they specifically also withdrawal consent to use of data already entered in the eCRF.

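### Protocol 14.5 makes investigator-judged non-adherence a ground for mandatory withdrawal without saying from what; on the better reading it conflicts with the follow-up rules in 14.6 and 24.5 and can cut endpoint follow-up informatively

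*Protocol*

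**What the plan says.** Protocol 14.5 opens with two levels of withdrawal: "Patients have the right to withdraw voluntarily from study treatment or the entire study at any time for any reason". Its mandatory list then drops the distinction: "A participant must be withdrawn if any of the following is present". The three triggers are withdrawal of consent, "Lack of adherence to the protocol as judged by the investigator", and taking part in another intervention study at the same time.

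Protocol 14.6 has a separate list for study drug only: "A participant must be discontinued in the IMP treatment if any of the following is present". Non-adherence is not on it. For patients who stop the drug, 14.6 says "After discontinuation of study medication in the randomized population, observation should continue with visits as planned in the observational group", with registries, hospitals, GPs or interviews as a fallback, "in order to monitor development of endpoints in all included patients as thoroughly as possible, provided that the patient agrees". Appendix 24.5 says that patients who discontinue study medication "will remain in the study and be followed for the full duration of the study".

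On the analysis side, SAP 5.4 states: "Participants who withdraw will be included in the analysis with exposure time from baseline to last observation". SAP 6.2 says that no method will be used for missing data and that nothing will be censored. Protocol 15.5 defines intention-to-treat as all randomised patients; SAP 4.3.3 defines it as high-risk patients who were given study medication.

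**The concern.** Two rules can apply to the same patient and point in opposite directions: one ends participation, the other continues endpoint observation. The deciding judgement is the investigator's and has no threshold, so it can vary between sites.

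Non-adherence arises after randomisation and may be related both to treatment and to risk. If it ends follow-up, the off-drug time that a treatment-policy estimate should count is lost. The loss is permanent: under Protocol 7.4 a patient withdrawn after starting study medication cannot re-enter. None of the SAP's sensitivity or additional analyses (6.3.1.3, 6.3.2.3, 6.4) addresses informative withdrawal. Protocol 15.6 left it to the SAP to say whether drop-outs before sampling count as treatment failures, and the SAP does not say. Because 14.5 covers all participants, the high- versus low-risk comparison is exposed too, although its size cannot be derived from the documents.

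**Working it through.** **1. What 14.5 means by withdrawal.**
- The list applies to any participant. About 85% of the cohort is expected to be low-risk (Protocol 6.2), and only the intervention group receives study drug (11.1). For low-risk participants, withdrawal can only mean leaving the study.
- Withdrawal of consent, in the same list, points the same way.
- Stopping drug alone has its own list and wording in 14.6, and 7.4 draws the same distinction.

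The text does not say so outright, but leaving the study is the better reading.

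**2. Whether one event can fall under both rules.** Lithium and potassium-sparing diuretics are prohibited by Protocol 12.2, so taking them departs from the protocol (14.5). The same drugs are listed in 14.6 as reasons to stop study drug, with observation continued. Likewise, tablet-taking outside the 80–110% range in 11.2 can be read as non-adherence, while 24.5 keeps patients off study drug in the study to the end. Nothing says which rule takes precedence.

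**3. The plan's own figure.** Inputs from Protocol 15.1: 40% placebo, 24% active, two-sided alpha 0.05, power 80% (printed as beta). The unpooled two-proportion formula gives

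n = (1.960 + 0.842)² × (0.40×0.60 + 0.24×0.76) / 0.16² = 129.5 per arm,

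which matches the stated 129. With 10% drop-out, 129/0.9 rounds up to 144 per arm, or 288 in total, which 300 covers. This point does not affect the sample size.

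**4. Equal non-adherence in both arms.** Constant hazards over follow-up of length 1: placebo −ln(0.60) = 0.511, active −ln(0.76) = 0.274, hazard ratio 0.537. Assumptions: 150 per arm; a fraction q of each arm is non-adherent from mid-study; non-adherers on active then return to the placebo hazard. Non-adherers' hazard is multiplied by m throughout. The Cox score equation was solved with everyone followed, and with follow-up ended at withdrawal.

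| q per arm | followed, m=1 | followed, m=1.5 | follow-up ended |
|---|---|---|---|
| 5% | 0.547 | 0.550 | 0.537 |
| 10% | 0.557 | 0.563 | 0.537–0.538 |
| 20% | 0.577 | 0.587 | 0.537–0.538 |
| 30% | 0.597 | 0.609 | 0.537–0.538 |

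Hand check for q = 10%, m = 1: the second-half ratio is about 0.9×0.537 + 0.1×1 = 0.583, and its average with 0.537 is 0.560, close to 0.557. Expected events fall from 97 to 92. With about 95 events, SE(log HR) ≈ 2/√95 = 0.205. The shift ln(0.557/0.537) = 0.037 is about 0.18 of a standard error.

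**5. Unequal non-adherence.** Large-sample simulation: 20,000 per arm, follow-up 2–4.4 years, on-drug hazard ratio 0.54, non-adherence recognised between 0.25 and 2 years.

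| Active / placebo non-adherent | Hazard multiplier | Followed | Follow-up ended |
|---|---|---|---|
| 10% / 10% | 1 | 0.562 | 0.538 |
| 10% / 5% | 2 | 0.593 | 0.542 |
| 15% / 5% | 2 | 0.632 | 0.553 |
| 5% / 15% | 2, throughout | 0.516 | 0.516 |
| 5% / 15% | 2, only after non-adherence | 0.535 | 0.540 |

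In the 15%/5% case the shift is ln(0.632/0.553) = 0.134, about 0.65 of a standard error on the same 0.205. With an inert drug and 10% non-adherent in each arm, the ratios are 0.999 and 0.996, so there is no material bias.

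**The case against.** The case against has four parts.

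- **The conflict depends on interpretation.** 14.5 does not say from what a participant is withdrawn, and the trigger is adherence to the protocol, not to tablets. A patient taken off drug under 14.6 or 24.5 may be following the protocol, and a site could stop the drug and carry on observing. This stands in part: the conflict is not certain. But the scope of the list and the overlap with prohibited medication make it likely, and a site has no text that settles it.
- **Tolerability is mostly handled elsewhere.** Unacceptable side effects and safety concerns lead to stopping drug with continued observation under 14.6, and hyperkalaemia is covered by Appendix 1. This stands. What remains under 14.5 is non-adherence not already handled that way, and nothing in the documents shows that it differs by arm.
- **The analysis set is unaffected.** A reader might infer that the comparison becomes one among adherers. The documents do not support that: neither intention-to-treat definition has an adherence condition, withdrawn patients count with their time and events to last observation, and SAP 4.3.4 defines adherers separately for the per-protocol cohort. Only follow-up is truncated.
- **The direction is not fixed.** A reader might infer that the rule always flatters spironolactone. The 5%/15% rows above show no bias, or a slight one against it.

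**Conclusion.** The concern holds as an unresolved conflict between 14.5 on one side and 14.6 and 24.5 on the other, with a possible informative loss of follow-up that the SAP does not examine. It rests on reading withdrawal in 14.5 as leaving the study, which the text favours but does not state.

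The size is conditional, because every non-adherence rate used is an assumption. At 10% per arm, in line with the 10% drop-out in Protocol 15.1 and the under-15% in 15.6, the hazard ratio moves from about 0.56 to 0.54, well inside sampling error. It matters more (0.63 to 0.55) only if non-adherence is markedly commoner on active and non-adherers are at higher risk. It is nil or reversed if non-adherence is commoner on placebo.

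SAP 5.4 and 6.2 also do not fit together. Ending exposure at the last observation is censoring in a Cox model, and 6.2 says there will be none.

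**What to change.** 1. Reconcile Protocol 14.5 with 14.6 and 24.5 so that investigator-judged non-adherence does not by itself end endpoint follow-up. Such participants continue UACR sampling and endpoint follow-up if they agree, and the deviation is recorded. What non-adherence means for study drug, and how concurrent participation in another trial is handled, are for the sponsor to reconcile. Concurrent participation is barred by exclusion criterion 21, and nothing here supports simply deleting that trigger.
2. Reconcile SAP 5.4 with 6.2 by stating the censoring rule for participants who leave.
3. Report investigator-initiated withdrawals by arm and by risk group.
4. If the number is not negligible, add a sensitivity analysis for informative withdrawal.

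The cost is low: wording, a note to sites, one table and possibly one further analysis. The visits are already scheduled. The downside is that some retained patients will have incomplete data. The SAP describes recruitment and the safety committee's reviews as past, so a protocol change may come too late to alter conduct. In that case items 2 to 4 are the working remedy.
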